6.1 Pre-visit Restrictions

The following restrictions in relation to dosing should be adhered to:

- Patients should refrain, where possible, from xanthine (chocolate, caffeine containing drinks and food), for at least 24 hours before and during all visits. Decaffeinated beverages are permitted
- Patients should refrain from alcohol for 24 hours before and during all visits (including visits for safety laboratory tests) and until all procedures for that study visit are completed
- Patients must fast (water permitted) from 2 hours pre-dose until 1 hour post-dose
- Patients should refrain from smoking from 1 hour pre-dose, and at least 1 hour before any measurement of lung function
- Patients should refrain from strenuous exercise for 72 hours prior to all study visits and should undertake no unaccustomed strenuous exercise from Screening until the end of study visit

6.2 Screening

Written informed consent will be obtained by the Investigator as specified in Section 10.3 prior to any study related procedures being performed. This typically will need to be performed prior to the Screening visit to allow for discontinuation of any prohibited medications (see Section 5.9). Screening procedures may be performed over more than 1 day.

Patients will be screened to determine eligibility against the Inclusion and Exclusion Criteria between 7 and 14 days before the first dose of study treatment. There are no fasting requirements for the Screening visit. Patients must observe the medication restrictions described in Section 5.9.1, and other restrictions described in Section 1.1To account for diurnal variability in pulmonary function, the Screening visit is to take place in the morning.

The following assessments will be performed, generally in the order indicated (to the extent feasible):

- Obtain informed consent (if not done prior to Screening)
- Recording of demographic information, including height and weight
- Recording of medical/surgical and disease history
- Recording of prior medications and therapies
- Vital signs
- Full physical examination (see Section 7.4.5)
- Alcohol breath test
- 12-lead ECG
- Chest X-ray (unless historical X-ray performed in last 12 months is available)
- Whole body plethysmography training and assessment of capacity to perform procedure (may be performed more than once as required)
- Pre-reversibility spirometry
- Reversibility test (two puffs salbutamol/albuterol followed by two puffs ipratropium)
- Post-reversibility spirometry (20 to 30 minutes after administration)
- Place 24-hour Holter monitor; patients will be instructed to return the next day for removal of the Holter monitor

Verona Pharma plc CONFIDENTIAL Page 35 of 66

- Blood and urine samples for laboratory safety tests (hematology, biochemistry, urinalysis), pregnancy tests (female patients of childbearing potential only), and viral serology. The urine pregnancy test result should be obtained prior to chest X-ray for females of childbearing potential.
- Instruct patients to stop all long acting bronchodilators for the duration of the study
- Inhalation training for use of nebulizer and Respimat[®]. This will be verbal instruction and demonstration of the device
- Questioning for adverse events

If the patient meets all of the Inclusion and none of the Exclusion Criteria, he/she will be instructed to return in 7 to 14 days for Treatment Period 1, Day 1.

6.3 Treatment Periods 1 through 3

Each treatment period is approximately 72 hours in duration. Patients will stay at the study center for the duration of each treatment period.

Patients must withhold long acting bronchodilators, ipratropium and salbutamol/albuterol (or Combivent®) prior to the start of the treatment period as defined in Section 5.9.1. If not, the start of the treatment period must be rescheduled so as to occur within the permitted windows. All restrictions defined in Section 1.1 should also be adhered to.

At the start of Treatment Period 1, patients will be evaluated to ascertain if the Inclusion and Exclusion Criteria are still met. If so, patients will receive a randomization number.

6.3.1 Day 1

6.3.1.1 Pre-Dose Assessments

The following assessments will be performed prior to dosing:

- Confirm that respiratory medications were withheld as required
- Questioning for adverse events
- Urine pregnancy test (females of childbearing potential only)
- 12-lead ECG
- Dyspnea scale
- Vital signs
- Brief physical examination (see Section 7.4.5)
- Spirometry; 1 hour (±5 minutes) and immediately prior to study treatment administration
- Whole body plethysmography
- Inhalation training

6.3.1.2 Study Treatment Administration

Patients will be dosed with open label tiotropium/olodaterol 5/5 μg (two inhalations, each containing 2.5 μg /2.5 μg), followed immediately (within 2 minutes) with either blinded RPL554 or placebo using a nebulizer according to randomization scheme. At 12 hours (± 30 minutes) after the morning dose, the second dose of RPL554 or placebo will be administered by nebulization.

Verona Pharma plc CONFIDENTIAL Page 36 of 66

6.3.1.3 Post-Dose Assessments (after morning doses only)

The following assessments will be performed, at the times indicated relative to dosing:

- Spirometry at 5 (\pm 1) minutes, 15 (\pm 5) minutes, 30 minutes and 1, 1.5, 2, 4, 6, 8 and 12 hours (the latter assessments all \pm 10 minutes)
- Whole body plethysmography at 1.25 hours (± 10 minutes)
- Vital signs at 30 minutes and 1, 2, 4, 6, 8 and 12 hours (± 10 minutes)
- 12-lead ECGs at 2 and 4 hours (±10 minutes)
- Dyspnea scale administered at 5 (\pm 1), 15 (\pm 5), and 30 (\pm 10) minutes
- Questioning for adverse events

6.3.2 Day 2

6.3.2.1 Pre-Dose Assessments

The following assessments will be performed prior to dosing:

- Questioning for adverse events
- 12-lead ECG
- Vital signs
- Spirometry

6.3.2.2 Study Treatment Administration

Patients will be dosed with open label tiotropium/olodaterol 5 μ g /5 μ g (two inhalations, each containing 2.5 μ g /2.5 μ g) followed immediately (within 2 minutes) with either blinded RPL554 or placebo using a nebulizer according to the randomization scheme. At 12 hours (± 30 minutes) after the morning dose, the second dose of RPL554 or placebo will be administered by nebulization.

6.3.2.3 Post-Dose Assessments (after morning dose only)

The following assessments will be performed, at the times indicated relative to dosing:

- 12-lead ECGs at 2 hours (±10 minutes)
- Vital signs at 30 minutes and 1, 2, 3, 4, 8 and 12 hours (± 10 minutes)
- Spirometry at 15 (\pm 5) and 30 minutes and 1, 2, 3, 4 and 12 hours (the latter assessments all \pm 10 minutes)
- Questioning for adverse events

6.3.3 Days 3 to 4

6.3.3.1 Pre-Dose Assessments

The following assessments will be performed prior to dosing:

- Questioning for adverse events
- 12-lead ECG
- Vital signs

Verona Pharma plc CONFIDENTIAL Page 37 of 66

- Spirometry
- Whole body plethysmography
- 24-hour Holter monitor placed
- Dyspnea scale
- Blood sample for pharmacokinetics

6.3.3.2 Study Treatment Administration

Patients will be dosed with open label tiotropium/olodaterol 5 μ g /5 μ g (two inhalations, each containing 2.5 μ g /2.5 μ g) followed immediately (within 2 minutes) with either blinded RPL554 or placebo using a nebulizer according to the randomization scheme. At 12 hours (± 30 minutes) after the morning dose, the second dose of RPL554 or placebo will be administered by nebulization.

6.3.3.3 Post-Dose Assessments

- 12-lead ECGs at 2 and 24 hours (±10 minutes)
- Vital signs at 30 minutes and 1, 2, 4, 6, 8 and 24 hours (± 10 minutes)
- Spirometry at 5 (\pm 1), 15 (\pm 5) and 30 minutes and 1, 1.5, 2, 4, 6, 8, 12, 13, 14, 16, 23 and 24 hours after the morning dose (the latter assessments all \pm 10 minutes)
- Whole body plethysmography at 1.25, 8.25 and 12.25 hours (± 10 minutes)
- Dyspnea scale at 5 (\pm 1), 15 (\pm 5), and 30 (\pm 10) minutes and 24 hours (\pm 10 minutes)
- Questioning for adverse events
- Blood samples for pharmacokinetics at 5 (\pm 1), 30 and 45 minutes and 1, 1.5, 2, 4, 8 and 12 hours (the latter assessments all \pm 10 minutes)
- Blood sample for laboratory safety tests (hematology and biochemistry) at 24 hours (±10 minutes)
- Brief physical examination prior to discharge (Day 4)

The 24-hour assessments will be performed in the morning on Day 4 prior to discharge from the study center.

Patients will be instructed to return in 7 to 14 days (taken from last dose of study medication on Day 3) for the next visit, or if Treatment Period 3, to return in 4 to 10 days (from Day 4) for the end of study visit. Early terminated patients should have an End of Study Visit.

6.4 End of Study Visit

The following will be performed:

- Full physical examination
- Vital signs
- Spirometry
- Blood and urine samples for laboratory safety tests (hematology, biochemistry, urinalysis)
- Urine pregnancy test (females of childbearing potential)
- 12-lead ECG
- Questioning for adverse events

Verona Pharma plc CONFIDENTIAL Page 38 of 66

7 STUDY METHODOLOGY

7.1 Demographics, Baseline Characteristics and Eligibility Assessments

Safety assessments (laboratory safety assessments, vital signs, 12-lead ECG and physical examination) will be performed at Screening as part of the eligibility assessment as described in Section 7.1.1 to Section 7.4.6.

7.1.1 Demographic Variables

Demographic variables, including date of birth, sex, height, weight, BMI (weight [kg]/height [m]²), race and smoking status will be collected at Screening.

7.1.2 Medical and Disease History

All active medical conditions and all surgeries will be recorded at Screening. Disease history, including date of diagnosis will also be recorded.

7.1.3 Reversibility Test

Reversibility in response to salbutamol/albuterol will be assessed at Screening as an eligibility measure. Spirometry (FEV1 and FVC) assessment before and after two puffs (200 μ g) of salbutamol/albuterol and two puffs (40 μ g) of ipratropium, each administered using a pMDI will be performed.

Three technically acceptable measurements should be made and recorded in the eCRF. Spirometry assessments may be performed up to eight times to obtain three acceptable readings according to ATS guidelines (Miller et al, 2005). The highest reading from each assessment will be used for calculation of predicted values and increase from baseline.

The following must be confirmed for inclusion:

- Post-bronchodilator FEV₁/FVC ratio of <0.70
- Post-bronchodilator FEV₁ ≥30 % and ≤70% of predicted normal*
- Demonstrates ≥150 mL increase from pre-bronchodilator FEV₁
- *National Health and Nutrition Examination Survey (NHANES) III (Hankinson et al, 1999) will be used as a reference for normal predicted values.

7.1.4 Screening Laboratory Assessments

At Screening, blood samples will be taken and tested at the laboratory for human immunodeficiency virus, hepatitis B and hepatitis C serology. Note: Patients who received a hepatitis B vaccination and are positive for hepatitis B surface antibody, but are negative for both hepatitis B surface antigen and hepatitis B core antibody, do not need to be excluded from the study.

A chest X-ray (post-anterior) must be performed at Screening or in the 12 months prior to Screening.

An alcohol breath test will be performed by the study center at Screening.

Unscheduled and/or repeat testing may be performed at the discretion of the Investigator.

Verona Pharma plc CONFIDENTIAL Page 39 of 66

7.1.5 Prior and Concomitant Medications and Therapies

Prior COPD therapies and medications will be recorded at Screening and concomitant use during the study recorded as described in Section 5.9.1.

Other prior medications will be separately recorded at Screening and concomitant use during the study recorded as described in Section 5.9.2.

7.1.6 Eligibility Check

Patients will be confirmed as eligible according to the Inclusion and Exclusion Criteria from assessments made at Screening with a final check of all results pre-dose in Treatment Period 1.

7.2 Efficacy/Pharmacodynamic Assessments

7.2.1 Pulmonary Function Tests

Spirometry (FEV₁ and FVC) will be performed at Screening, the end of study visit and the following time points in each treatment period:

- Day 1: 1 hour and immediately pre-dose; 5, 15 and 30 minutes and 1, 1.5, 2, 4, 6, 8 and 12 hours post-dose
- Day 2: pre-dose; 15 and 30 minutes and 1, 2, 3 4 hours and 12 hours post-dose
- Day 3: pre-dose; 5, 15 and 30 minutes and 1, 1.5, 2, 4, 6, 8, 12, 13, 14, 16, 23 and 24 hours post-dose.

Post-dose measurements will be taken in relation to the morning dose of tiotropium/olodaterol and RPL554 or placebo. The 12-hour measurement will therefore be taken pre-dose before the evening dose of RPL554 or placebo. The 24-hour measurement on Day 3 will be taken in the morning on Day 4 prior to discharge from the study center.

Spirometry assessments will be made in accordance with ATS/ERS guidelines (Miller et al, 2005). At all timepoints, three technically acceptable measurements should be made and recorded. Spirometry assessments may be performed up to eight times to obtain three acceptable readings. The highest FEV_1 and FVC readings from each assessment will be used for analysis even if the FEV_1 and FVC values come from two different forced exhalations.

7.2.2 Whole Body Plethysmography

Whole body plethysmography training and assessment for ability to perform the procedure will be conducted at Screening.

Whole body plethysmography will be performed pre-dose and 1.25 hours post-dose on Day 1, and pre-dose and 1.25, 8.25 and 12.25 hours post-dose on Day 3 of each treatment period. Assessments will be made in accordance with ATS/ERS guidelines, including the use of appropriate quality control measures to minimize data variability and error (Wanger et al, 2005; see Quality Control section for plethysmography on pp. 514-515).

Patients will be placed on a body box for plethysmographic determination of lung volumes, to include RV and FRC. Additionally, measurements will be made of sG_{aw}.

7.2.3 Dyspnea Scale

An 11-point Likert scale will be utilized, which will be anchored from 0: "no shortness of breath" to 10: "the worst shortness of breath that you can imagine" (Davis et al., 2006). This

Verona Pharma plc CONFIDENTIAL Page 40 of 66

scale will be an instantaneous measurement of their dyspnea at that moment, and not reflective. It will be administered on Day 1 pre-dose and 5, 15, and 30 minutes post-dose; and on Day 3 pre-dose and 5, 15, 30 minutes and 24 hours post-dose.

7.3 Pharmacokinetic Assessments

Pharmacokinetic analysis will be performed on samples taken from patients on Day 3 of each treatment period. Blood samples (4 mL at each time point) will be collected at the following timepoints: pre-dose, 5, 30 and 45 minutes and 1, 1.5, 2, 4, 8, and 12 hours post-dose.

Samples will be collected by venipuncture or via indwelling cannula in the forearm into lithium heparin tubes and will be immediately chilled (ice bath). The blood will be centrifuged within 15 minutes of collection. The plasma will be separated in a refrigerated centrifuge (about 4°C) at 1100g for 15 minutes and transferred into polypropylene tubes. After each blood collection, the plasma will be dispensed into two aliquots. After appropriate labelling, the plasma samples will be stored at, or below -20°C. The plasma samples will then be transported in dry ice to an external laboratory where they will be stored at or below -20°C until they are submitted for analysis with a validated method. Analysis will be performed by a central laboratory.

7.4 Safety Assessments

7.4.1 Adverse Events

7.4.1.1 Adverse Event Definitions

An adverse event is defined as any undesirable experience occurring to a patient, or worsening in a patient, during a clinical study, whether or not considered related to the study medication. An adverse event may be any of the following:

- A new illness
- An exacerbation of a sign or symptom of the underlying condition under treatment or of a concomitant illness
- Unrelated to participation in the clinical study or an effect of the study medication
- A combination of one or more of the above factors

No causal relationship with the study medication is implied by the use of the term "adverse event." An exacerbation of a pre-existing condition or illness is defined as a more frequent occurrence or as an increase in the severity of the pre-existing condition or illness during the study. Planned or elective surgical or invasive procedures for pre-existing conditions that have not worsened are not adverse events. However, any complication that occurs during a planned or elective surgery is an adverse event (if the event fits the serious criteria, such as an extended hospitalization, it will be considered to be serious). Conditions leading to unplanned surgical procedures may be adverse events.

An adverse reaction is defined as all untoward and unintended responses to study medication related to any dose administered.

A serious adverse event (SAE) is any adverse experience that:

- Results in death
- Is life-threatening
- Requires inpatient hospitalization or prolongation of existing hospitalization
- Results in persistent or significant disability/incapacity, OR

Verona Pharma plc CONFIDENTIAL Page 41 of 66

- Is a congenital anomaly/birth defect
- Other medical events*

*Important medical events that may not be immediately life-threatening or result in death or hospitalization may be considered a SAE when, based on appropriate medical judgement, they may jeopardize the patient or may require medical or surgical intervention to prevent one of the outcomes listed above.

An unexpected adverse reaction is an adverse reaction in which the nature or severity of which is not consistent with the Investigator Brochure.

A suspected unexpected serious adverse reactions (SUSAR) is any suspected adverse reaction related to the study medication that is both unexpected and serious.

Standard procedures for emergency care should be followed for any individual adverse event, whenever clinically needed (decision to be taken by the Investigator).

7.4.1.2 Recording and Assessing Adverse Events

All adverse events, whether reported spontaneously by the patient, in response to open questioning on treatment days or observed by the Investigator or his/her staff, will be recorded from informed consent until the end of study visit. The start and stop time will be recorded and adverse events will be assessed by the Investigator for the following:

7.4.1.2.1 Severity

Mild: Resolved without treatment

Moderate: Resolved or was tolerated with specific treatment without affecting study

activities

Severe: Did not resolve or was not tolerated with treatment

7.4.1.2.2 *Chronicity*

Single occasion: Single event with limited duration

Intermittent: Several episodes of an event, each of limited duration

Persistent: Event which remained indefinitely

7.4.1.2.3 *Causality*

The Investigator will assess causal relationship between the study medication and each adverse event, and answer "yes" or "no" to the question, "Do you consider that there is a reasonable possibility that the event may have been caused by the study medication?"

For SAEs, causal relationship will also be assessed for study procedures, additional study medication, and other medication. Note that for SAEs that could be associated with any study procedure, the causal relationship is implied as "yes".

A guide to the interpretation of the causality question is found in Section 14.3.

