4.3 Removal of Patients from Therapy or Assessment

4.3.1 Study Treatment Discontinuation

Study treatment must be discontinued for the following reasons:

- Unacceptable toxicity related to study treatment
- Intolerable or persistent adverse events of any severity
- General or specific changes in the patient's condition rendering the patient unacceptable for further treatment in the judgment of the Investigator
- Clinically significant progression of disease
- Pregnancy in a female patient

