7.4.1.2.4 Action and Outcome

• Action taken with study medication (none, study medication stopped, study medication temporarily interrupted)

Verona Pharma plc CONFIDENTIAL Page 42 of 66

- Other actions (none, concomitant medication, study discontinuation, hospitalization, other)
- The outcome and date of outcome according to the following definitions:
 - Recovered or resolved (adverse event disappeared)
 - Recovering or resolving (patient is recovering)
 - Not recovered or not resolved (adverse event remains without signs of improvement)
 - Recovered or resolved with sequelae (adverse event has resulted in permanent disability or incapacity)
 - Fatal
 - Unknown (only applicable if patient has been lost to follow-up)
- Seriousness (yes or no)

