9.4.7 Safety

Safety data including safety laboratory tests, 12-lead ECG and Holter parameters, vital signs and physical examinations, will be summarized by treatment group and time point of collection, when appropriate. For continuous variables, the change from baseline (pre-dose at each treatment period) to each post-dose time point will also be calculated and summarized. Data will further be illustrated by shift tables (showing changes from low/normal/high) and shift

Verona Pharma plc CONFIDENTIAL Page 51 of 66

plots for selected time points. Separate listings will be generated of abnormal values occurring after the first dose of study treatment.

Coded adverse event terms will be presented by system organ class (SOC) and preferred term and summarized by treatment group. A summary table by treatment group with total number and number of patients with adverse events, SAEs, adverse events leading to discontinuation of study treatment, causally related adverse events and severe adverse events will be produced. Further, SAEs, causally related adverse events and adverse event of each intensity will be summarized by SOC and preferred term.

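### Adverse event severity is graded mainly by resolution and treatment, so the planned severity tables would not measure intensity

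*Protocol*

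**What the plan says.** Protocol 7.4.1.2.1 has three grades:

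- The first is "Mild: Resolved without treatment".
- Moderate is an event that "Resolved or was tolerated with specific treatment without affecting study" activities.
- Severe is an event that "Did not resolve or was not tolerated with treatment".

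The sections that follow record overlapping information in separate fields:

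- **Chronicity (7.4.1.2.2)** includes "Persistent: Event which remained indefinitely".
- **Outcome (7.4.1.2.4)** includes "Not recovered or not resolved (adverse event remains without signs of improvement".
- **Action (7.4.1.2.4)** includes "Other actions (none, concomitant medication, study discontinuation, hospitalization, other".

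The grade is then used in the analysis. Protocol 9.4.7 counts severe adverse events and tabulates "adverse event of each intensity". SAP 16.1.1 breaks treatment-emergent events down by maximum severity. SAP 16.1.1.1 treats the three grades as an ascending scale, keeps the worst grade per patient within a term, and sets a missing grade to severe for treatment-emergent events that start after first dose. The SAP gives no definition of its own. Elsewhere, Protocol 4.3.1 refers to "Intolerable or persistent adverse events of any severity".

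**The concern.** A severity grade is expected to say how bad an event was. Here it says mainly whether the event went away and whether it was treated. Both facts are already recorded elsewhere, so the field adds little, and intensity alone never sets the grade.

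At stake are the tolerability tables, which serve a stated secondary objective (Protocol 2.2) and a listed endpoint (Protocol 9.3.2). Protocol 1.2 names headache, cough, dizziness and palpitations as the most common events so far. For symptoms such as headache and dizziness, the severity grade is the only place where the plan could record intensity. With this definition, the tables would reflect willingness to treat and the state of the event when it was graded.

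**Working it through.** No arithmetic applies. The check applies the three definitions to concrete cases and then follows the grade into the tables.

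**Step 1: is there another definition?** Both documents were searched and neither has one. Protocol 7.4.1.2.1 governs by default.

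**Step 2: apply the definitions.** The Severe line can be read in two ways. On the plain reading, *with treatment* qualifies only the second half, so non-resolution alone is enough. On the narrower reading it qualifies both halves, in parallel with the Moderate line.

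| Case | Mild? | Moderate? | Severe? | Result |
|---|---|---|---|---|
| Intense, ends by itself, untreated | Yes | No, no specific treatment | No, it resolved and was untreated | Mild |
| Trivial, ends by itself, untreated | Yes | No | No | Mild, as for the intense event |
| Trivial, untreated, not resolved when graded | No | No | Yes (plain); no (narrower) | Severe, or no grade |
| Not resolved, treated, tolerated, study activities unaffected | No | Yes | Yes, on either reading | Two grades fit |

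The first two rows differ only in intensity and receive the same grade. In the third row, the narrower reading leaves a gap. If the investigator leaves the field blank for an event that started after first dose, SAP 16.1.1.1 makes it severe, so both readings can end in the same table cell. In the fourth row, two investigators who both follow the text can grade the same event differently.

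**Step 3: what does the grade add to the other fields?** Mild corresponds to a recovered outcome with no treatment given. The non-resolution half of Severe corresponds to an unrecovered outcome. What remains is whether a treated event was tolerated and whether it affected study activities. For untreated events nothing remains.

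**Step 4: where does the grade go?**

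- *Severe-event counts and by-intensity tables (Protocol 9.4.7):* affected directly.
- *Maximum-severity tables (SAP 16.1.1 and 16.1.1.1):* affected directly, because the worst-grade rule assumes an ordering that the definitions do not supply.
- *Treatment emergence (SAP 16.1):* the definition mentions worsening in severity, but the algorithm in SAP Appendix 2 assigns status from start and stop dates only. Counts under that algorithm do not change.
- *Efficacy, power and type I error:* these do not use the grade.

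**The case against.** The other side has a substantial case, and much of it limits the point.

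**The scale is not wholly blind to impact.** Tolerance and effect on study activities are tolerability and function terms, and they can be judged while an event is still open. This stands, so it would be wrong to say that the scale captures nothing of the kind or that grading must wait for the outcome. But these terms apply only to treated events.

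**Protocol 4.3.1.** A reader might infer a flat contradiction, on the ground that a persistent event can only be Severe. The text does not support that, because a persistent event tolerated on treatment can be Moderate. What remains is awkward wording: 4.3.1 treats severity as separate from tolerability and persistence, while 7.4.1.2.1 builds severity partly out of them.

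**Protocol 9.4.7.** The word intensity there is probably a loose synonym for the same grade. It is not evidence of a second scale. The table would still promise something the grade does not measure.

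**The end-of-study visit.** A reader might infer that every event still open at that visit becomes Severe. The grade is not tied to that visit, Protocol 7.4.1.3 follows events until they abate or stabilize, and some open events qualify as Moderate.

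**Cardiovascular signals.** A reader might infer that tachycardia or hypotension would be hidden as Mild. The documents do not call those signals typically transient; Protocol 1.2 uses that word for dizziness. It places the small heart-rate increases at 12 to 24 mg, above the 1.5 and 6 mg studied here. Blood pressure, pulse, ECG and Holter data are collected independently of the grade, and seriousness has its own field and criteria.

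**No differential bias is shown.** One definition applies to all three treatments under double blinding, and SAP 16 plans no between-treatment safety tests unless specified. This stands. The point is that the tables measure the wrong thing, not that they favor a treatment.

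**Conclusion.** The point holds as a defect of definition. The plan states a rule which, when followed, gives intense self-limiting events the lowest grade. It can give trivial unresolved events the highest grade or none, and it lets some treated events fall into two grades. The planned severity tables would therefore not measure intensity.

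The size is confined to the severe-event counts and the by-intensity and maximum-severity tables. The share of events misgraded cannot be derived from the documents, because it depends on how many events resolve untreated and how many are open when graded, and neither is given.

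The Mild result for an intense untreated event takes the Moderate line as requiring treatment for both of its halves; otherwise that line would also cover every Mild event. The Severe result for a trivial untreated event depends on the plain reading, and the alternative leaves a gap in the scale. The conclusion also assumes that investigators follow the protocol wording. The eCRF completion guidance is not among the documents and might say something else.

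**What to change.** Define mild, moderate and severe in Protocol 7.4.1.2.1 by the intensity of the event itself, for example by degree of interference with usual activity. State that the grade is assigned independently of outcome, duration and treatment, which stay in their existing fields. Put the same definition in SAP 16.1.1.1 and in the eCRF guidance. Use one term, severity or intensity, throughout Protocol 9.4.7. Reconcile the wording of Protocol 4.3.1 with the revised scale; this concerns consistency of terms only and implies no change to when treatment is stopped.

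The cost is protocol, SAP and eCRF guidance wording, with no new data field or assessment. The planned study period is June to December 2018 and the SAP is dated 18 October 2018, so some events may already have been graded. If so, the severity tables should carry a footnote giving the definition under which those events were graded.
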